**CONFIDENTIAL PROTOCOL**

A Randomized, Double-Blind, Parallel-Design, Multiple-Site Study to Evaluate the Therapeutic Equivalence of Permethrin Cream, 5% (Encube Ethicals) Compared to Elimite™ Cream (permethrin) 5% (Prestium Pharma, Inc.) in the Treatment of Scabies

---

**14.3 APPENDIX C: PRODUCT INSERT FOR ELIMITE™**

**CONFIDENTIAL PROTOCOL**

A Randomized, Double-Blind, Parallel-Design, Multiple-Site Study to Evaluate the Therapeutic Equivalence of Permethrin Cream, 5% (Encube Ethicals) Compared to Elimite™ Cream (permethrin) 5% (Prestium Pharma, Inc.) in the Treatment of Scabies

---

**14.4 APPENDIX D: AMENDMENTS TO THE PROTOCOL**

Amendment	Date
1	10/31/2017

The following revisions were made to the protocol dated 05/02/2017.

[figure not shown]
- Removed Yates’ correction in the primary analysis.
- Removed the secondary endpoint and related analysis language.
- Added supportive analyses.
- Revised the PP population and Safety population inclusion criteria.
- Added justification for the change in statistics and deviation from the FDA guidance.
- Made minor typographical corrections throughout the document.

**ELIMITE™ CREAM**  
\*W/W  
Rx Only  
(PERMETHRIN) 5%\*

**DESCRIPTION**

ELIMITE™ (permethrin) 5% Cream is a topical scabicide agent for the treatment of infestation with *Sarcoptes scabiei* (scabies). It is available in an off-white, vanishing cream base. ELIMITE™ (permethrin) 5% Cream is for topical use only.

**Chemical Name** - The permethrin used is an approximate 1:3 mixture of the cis and trans isomers of the pyrethroid 3-(2,2-dichloroethyl)-2,2-dimethylcyclopropanecarboxylic acid, (3-phenoxyphenyl) methyl ester. Permethrin has a molecular formula of  $C_{21}H_{29}Cl_2O_3$  and a molecular weight of 391.29. It is a yellow to light orange-brown, low melting solid or viscous liquid.

**Active Ingredient** - Each gram contains permethrin 50 mg (5%).

**Inactive Ingredients** - Butylated hydroxytoluene, carbomer homopolymer type B, fractionated coconut oil, glycerin, glyceryl monostearate, isopropyl myristate, lanolin alcohols, mineral oil, polyoxyethylene cetyl ethers, purified water, and sodium hydroxide. Formaldehyde 1 mg (0.1%) is added as a preservative.

**CLINICAL PHARMACOLOGY**

Permethrin, a pyrethroid, is active against a broad range of pests including lice, ticks, fleas, mites, and other arthropods. It acts on the nerve cell membrane to disrupt the sodium channel current by which the polarization of the membrane is regulated. Delayed repolarization and paralysis of the pests are the consequences of this disturbance.

Permethrin is rapidly metabolized by ester hydrolysis to inactive metabolites which are excreted primarily in the urine. Although the amount of permethrin absorbed after a single application of the 5% cream has not been determined precisely, data from studies with  $^{14}C$ -labeled permethrin and absorption studies of the cream applied to patients with moderate to severe scabies indicate it is 2% or less of the amount applied.

**INDICATIONS AND USAGE**

ELIMITE™ (permethrin) 5% Cream is indicated for the treatment of infestation with *Sarcoptes scabiei* (scabies).

**CONTRAINDICATIONS**

ELIMITE™ (permethrin) 5% Cream is contraindicated in patients with known hypersensitivity to any of its components, to any synthetic pyrethroid or pyrethrin.

**WARNINGS**

If hypersensitivity to ELIMITE™ (permethrin) 5% Cream occurs, discontinue use.

**PRECAUTIONS**

**General** - Scabies infestation is often accompanied by pruritus, edema, and erythema. Treatment with ELIMITE™ (permethrin) 5% Cream may temporarily exacerbate these conditions.

**Information for Patients** - Patients with scabies should be advised that itching, mild burning and/or stinging may occur after application of ELIMITE™ (permethrin) 5% Cream. In clinical trials, approximately 75% of patients treated with ELIMITE™ (permethrin) 5% Cream who continued to manifest pruritus at 2 weeks had cessation by 4 weeks. If irritation persists, they should consult their physician. ELIMITE™ (permethrin) 5% Cream may be very mildly irritating to the eyes. Patients should be advised to avoid contact with eyes during application and to flush with water immediately if ELIMITE™ (permethrin) 5% Cream gets in the eyes.

**Carcinogenesis, Mutagenesis, Impairment of Fertility** - Six carcinogenicity bioassays were evaluated with permethrin, three each in rats and mice. No tumorigenicity was seen in the rat studies. However, species-specific increases in pulmonary adenomas, a common benign tumor of mice of high spontaneous background incidence, were seen in the three mouse studies. In one of these studies there was an increased incidence of pulmonary alveolar-cell carcinomas and benign liver adenomas only in female mice when permethrin was given in their food at a concentration of 5000 ppm. Mutagenicity assays, which give useful correlative data for interpreting results from carcinogenicity bioassays in rodents, were negative. Permethrin showed no evidence of mutagenic potential in a battery of *in vitro* and *in vivo* genetic toxicity studies.

Permethrin did not have any adverse effect on reproductive function at a dose of 180 mg/kg/day orally in a three-generation rat study.

**Pregnancy: Teratogenic Effects: Pregnancy Category B** - Reproduction studies have been performed in mice, rats, and rabbits (200 to 400 mg/kg/day orally) and have revealed no evidence of impaired fertility or harm to the fetus due to permethrin. There are, however, no adequate and well-controlled studies in pregnant women. Because animal reproduction studies are not always predictive of human response, this drug should be used during pregnancy only if clearly needed.

**Nursing Mothers** - It is not known whether this drug is excreted in human milk. Because many drugs are excreted in human milk and because of the evidence for tumorigenic potential of permethrin in animal studies, consideration should be given to discontinuing nursing temporarily or withholding the drug while the mother is nursing.

**Pediatric Use** - ELIMITE™ (permethrin) 5% Cream is safe and effective in pediatric patients two months of age and older. Safety and effectiveness in infants less than two months of age have not been established.

**Geriatric Use** - Clinical studies of ELIMITE™ (permethrin) 5% Cream did not identify sufficient numbers of subjects aged 65 and over to allow a definitive statement regarding whether elderly subjects respond differently from younger subjects. Other reported clinical experience has not identified differences in responses between the elderly and younger patients. This drug is known to be substantially excreted by the kidney. However, since topical permethrin is metabolized in the liver and excreted in the urine as inactive metabolites, there does not appear to be an increased risk of toxic reactions in patients with impaired renal function when used as labeled.

#### ADVERSE REACTIONS

In clinical trials, generally mild and transient burning and stinging followed application with ELIMITE™ (permethrin) 5% Cream in 10% of patients and was associated with the severity of infestation. Pruritus was reported in 7% of patients at various times post-application. Erythema, numbness, tingling, and rash were reported in 1 to 2% or less of patients (see **PRECAUTIONS-General**). Other adverse events reported since marketing ELIMITE™ (permethrin) 5% Cream include: headache, fever, dizziness, abdominal pain, diarrhea and nausea and/or vomiting. Although extremely uncommon and not expected when used as directed (see **DOSAGE AND ADMINISTRATION**), rare occurrences of seizure have been reported. None have been medically confirmed as associated with ELIMITE™ treatment.

#### OVERDOSAGE

No instance of accidental ingestion of ELIMITE™ (permethrin) 5% Cream has been reported. If ingested, gastric lavage and general supportive measures should be employed. Excessive topical use (see **DOSAGE AND ADMINISTRATION**) may result in increased irritation and erythema.

#### DOSAGE AND ADMINISTRATION

**Adults and children** -Thoroughly massage ELIMITE™ (permethrin) 5% Cream into the skin from the head to the soles of the feet. Scabies rarely infests the scalp of adults, although the hairline, neck, temple, and forehead may be infested in infants and geriatric patients. Usually 30 grams is sufficient for an average adult. The cream should be removed by washing (shower or bath) after 8 to 14 hours. Infants should be treated on the scalp, temple, and forehead. **ONE APPLICATION IS GENERALLY CURATIVE.**

Patients may experience persistent pruritus after treatment. This is rarely a sign of treatment failure and is not an indication for retreatment. Demonstrable living mites after 14 days indicate that retreatment is necessary.

#### HOW SUPPLIED

ELIMITE™ 5% Cream is available as follows:  
60 g tube (NDC 40076-230-60)

#### STORAGE

Store at 20-25°C (68-77°F) [see USP Controlled Room Temperature].

Manufactured for Prestium Pharma, Inc.  
Newtown, PA 18940

Manufactured by DPT Laboratories, Ltd.,  
San Antonio, TX 78215

Rev. 08/15

**NOVUM PHARMACEUTICAL RESEARCH SERVICES
STATISTICAL ANALYSIS PLAN**

Permethrin Cream, 5%

Protocol / Study No. 71675502

**NOVUM PHARMACEUTICAL RESEARCH SERVICES
STATISTICAL ANALYSIS PLAN**

Permethrin Cream, 5%

Protocol / Study No. 71675502

1. INTRODUCTION

This Statistical Analysis Plan (SAP) is based on the final Clinical Study Protocol 71675502 [Rev 1] dated 10/31/2017. The SAP provides details on the planned statistical methodology for the analysis of the study data. The SAP also outlines the statistical programming specifications for the tables, listings and figures.

This SAP describes the study endpoints, derived variables, anticipated data transformations and manipulations, and other details of the analyses not provided in the study protocol. This SAP therefore outlines in detail all other aspects pertaining to the planned analyses and presentations for this study.

The following documents were reviewed in preparation of this SAP:

- Final Clinical Study Protocol 71675502 [Rev 1] dated 10/31/2017.
- Case Report Form Booklet Version 1.0 for Novum Study No. 71675502

The reader of this SAP is encouraged to also read the clinical protocol for details on the conduct of this study, and the operational aspects of clinical assessments and timing for completing a patient in this study.

2. OBJECTIVES

The objectives of this study are to:

1. Evaluate the therapeutic equivalence of the Test formulation, Permethrin Cream, 5% (Encube Ethicals) to the marketed product, Elimite™ Cream (permethrin) 5% (Prestium Pharma, Inc.) in patients with scabies.
2. Compare the safety of Test and Reference treatments in patients with scabies.

3. OVERALL STUDY DESIGN

This randomized, double-blind, parallel-design, multiple-site study is designed to evaluate the therapeutic efficacy and safety of a generic Permethrin Cream, 5% (Encube Ethicals) compared to the FDA Reference Listed Drug (RLD), Elimite™ Cream (permethrin) 5% (Prestium Pharma, Inc.) in patients with scabies.

Before any study-specific procedures are performed, all patients will read and sign the IRB-approved informed consent that meets all criteria of current FDA and International Conference of Harmonisation (ICH) regulations. For patients who are considered minors in the state the study is being conducted (< 18 years in most states) the parent or legal guardian should sign the consent form and the child will be required to sign a patient “assent” form, as appropriate. Patients 11-17 years of age will read and sign an IRB-approved assent form and patients 6-10

NOVUM PHARMACEUTICAL RESEARCH SERVICES
STATISTICAL ANALYSIS PLAN

Permethrin Cream, 5%

Protocol / Study No. 71675502

years of age will provide verbal assent. Patients 2-5 years of age will be exempt from providing assent based on the child's comprehension and cognitive skills.

Approximately 250 eligible patients, 2 years of age and older with a clinical diagnosis of active scabies based on signs and symptoms and confirmation of microscopic evidence of scabies mites in the skin will be randomized in a 1:1 ratio (Test: Reference) to one of the two study products as follows:

- Test: Permethrin Cream, 5%, (Encube Ethicals)
- Reference: Elimite™ Cream (permethrin) 5% (Prestium Pharma, Inc.)

Patients will be instructed to self-administer a single dose of study product or, if patient is a child, then parent/guardian will apply study product to him/her on Day 1 according to the dosing instructions provided. A second application may be required if presence of scabies infestation is microscopically demonstrated (i.e., living mites, viable mite eggs, or mite fecal matter present) at Visit 2. The second dose will be self-administered by the patient or if patient is a child, then parent/guardian will apply study product to him/her at Visit 2. Eligible household members and close contacts of the patient will be offered permethrin cream (if they are in need of treatment) as a method to reduce cross-contamination within a household. Additionally, household members will be requested to follow the standard hygiene practices. Patients whose household members are not willing to comply with the standard of care for Scabies management (i.e., use of generic permethrin cream and standard hygiene practices) will not be enrolled in the study.

During the study, patients will visit the clinical center for a total of three scheduled visits:

- Visit 1 (Day 1): Screening/Baseline
- Visit 2 (Day 14 ± 4): Interim Visit
- Visit 3 (Day 28 ± 4): End of Study or Early Termination

Final assessments will be carried out at Visit 3 (Day 28 ± 4), which is the test-of-cure visit. The test-of-cure visit will occur 4 weeks (± 4 days) after the end of the single application treatment on study Day 1 or 2 weeks (± 4 days) after the end of a second application, if necessary, on study Visit 2. Therapeutic cure of scabies will be evaluated based on microscopic evidence of absence of scabies infestation (i.e., no living mites, no viable mite eggs, and no mite fecal matter), visual evidence of absence of new lesions and healing of original lesions, regardless of the presence of post-scabetic nodules (i.e., post-scabetic nodules need not be considered as new lesions or persistence of old lesions). The primary statistical analysis of interest is the proportion of patients in each treatment group with therapeutic cure (parasitological cure plus clinical cure) of scabies.

**NOVUM PHARMACEUTICAL RESEARCH SERVICES
STATISTICAL ANALYSIS PLAN**

Permethrin Cream, 5%

Protocol / Study No. 71675502

Figure 1 Study Schematic

	Visit 1 Screening/Baseline (Day 1)	Visit 2 Interim Visit (Day 14 ± 4)	Visit 3 (Day 28 ± 4) End of Study or Early Termination
Informed Consent	X		
Medical history and Baseline Demographics	X		
Vital Signs	X		X
Adverse Events	X	X	X
Concomitant Medications	X	X	X
Microscopic Examination	X	X	X
Scabies Signs and Symptoms Rating (pruritus, lesion count)	X	X	X
Urine Pregnancy Test	X		X
Review Inclusion/Exclusion Criteria	X		
Collect and Review Diary		X	X
Provide Diary	X	X	
Dispense Study Product	X	X*	
Collect and Weigh Study Product		X	X*

*If retreatment is necessary, the originally dispensed (i.e., at Visit 1) study product will be dispensed at Visit 2 and collected at Visit 3.

**NOVUM PHARMACEUTICAL RESEARCH SERVICES
STATISTICAL ANALYSIS PLAN**

Permethrin Cream, 5%

Protocol / Study No. 71675502

4. RANDOMIZATION AND BLINDING

The study product will be randomized, packaged and blinded by an independent packaging company. Randomization will be pre-planned according to a computer-generated randomization schedule. All randomized study products will be blinded and packaged in sealed boxes. Each block will contain two patients' worth of product (1 Test and 1 Reference). Each patient kit will include 1 x 60 gram tube of study product, which should be sufficient for full treatment.

The randomization number will be a unique four-digit number. Patient numbers will be assigned immediately before dispensing of study product and in ascending sequential order, beginning with the lowest available number at the study site. Each patient kit and each dispensed study tube should include the four-digit patient number on the label.

At the end of the study, after all the clinical data have been entered and the study database has been locked, a copy of the randomization schedule will be sent to the statistician.

The Investigator, staff at the study site, study monitors, and data analysis/management personnel will be blinded to the patient assignment.

5. SAMPLE SIZE

For the primary endpoint analysis (proportion of patients in the PP population who are considered to be a Therapeutic Cure on Day 28 ± 4), sample size is estimated for therapeutic equivalence of the Test to the Reference product.

Based on data from a previous bioequivalence study conducted to support approval of the first generic product of permethrin cream, 5%, the therapeutic cure rate (p_R) of the Reference product (Elimite™ permethrin cream 5%) is expected to be about 88% in the PP population. Assuming that the Therapeutic Cure rate for the Test group (p_T) is an absolute difference of 5% lower than the Reference group (i.e., $p_T - p_R = -5\%$), a sample size of 107 patients in each active group in PP population will provide at least 90% power to demonstrate therapeutic equivalence (i.e., the 90% confidence interval [Yates' continuity corrected] on $p_T - p_R$ is within a defined equivalence range [-20%, +20%]).

To allow for approximately 14 % of patients who may drop out from the study or are otherwise non-evaluable, approximately 250 patients (125 in each treatment group) will be randomized, such that there will be an estimated 214 patients (107 per group) in the PP population for statistical evaluation of therapeutic equivalence.

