**CONFIDENTIAL PROTOCOL**

A Randomized, Double-Blind, Parallel-Design, Multiple-Site Study to Evaluate the Therapeutic Equivalence of Permethrin Cream, 5% (Encube Ethicals) Compared to Elimite™ Cream (permethrin) 5% (Prestium Pharma, Inc.) in the Treatment of Scabies

---

	
given alternative therapy for their condition.
 
Concomitant medication use during the study will be tabulated by patient and by treatment.
 
All patients who are randomized to the active treatment period of the study who received study product will be included in the comparative safety analysis.

Sample Size Determination	
For the primary endpoint analysis (proportion of patients in the PP population who are considered to be a Therapeutic Cure on Day 28 ± 4), sample size is estimated for therapeutic equivalence of the Test to the Reference product.
 
Based on data from a previous bioequivalence study conducted to support approval of the first generic product of permethrin cream, 5%, the Therapeutic Cure rate (<math>p_R</math>) of the Reference product (Elimite™ permethrin cream 5%) is expected to be about 88% in the PP population. Assuming that the Therapeutic Cure rate for the Test group (<math>p_T</math>) is an absolute difference of 5% lower than the Therapeutic Cure rate for the Reference group (i.e., <math>p_T - p_R = -5\%</math>), a sample size of 107 patients in each active group in PP population will provide at least 90% power to demonstrate therapeutic equivalence (i.e., the 90% confidence interval [Yates' continuity-corrected] on <math>p_T - p_R</math> is within a defined equivalence range [-20% to +20%]).
 
To allow for approximately 14% of patients who may drop out from the study or are otherwise non-evaluable, approximately 250 patients (125 in each treatment group) will be randomized, such that there will be an estimated 214 patients (107 per group) in the PP population for statistical evaluation of therapeutic equivalence.

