## CONFIDENTIAL PROTOCOL

### A Randomized, Double-Blind, Parallel-Design, Multiple-Site Study to Evaluate the Therapeutic Equivalence of Permethrin Cream, 5% (Encube Ethicals) Compared to Elimite™ Cream (permethrin) 5% (Prestium Pharma, Inc.) in the Treatment of Scabies

---

absorption studies of the cream applied to patients with moderate to severe scabies indicate it is 2% or less of the amount applied. As the systemic absorption of the Reference product, Elimite™ cream (permethrin) 5% is extremely low, its relevance to clinical activity is not significant. A therapeutic efficacy evaluation based on relief from scabies symptoms and eradication of living mites in the skin after using study products is considered the most appropriate methodology for this study.

A previous bioequivalence study conducted for the FDA marketing approval for the first generic product of permethrin cream, 5% indicated that the rate of clinical cure for this product and that for the Reference product, Elimite™ cream (permethrin) 5%, was about 88%; there was no placebo treatment arm in that study.

The design and sample size estimation for the study described in this protocol are based on a previous bioequivalence study.

The FDA published a Draft Guidance on Permethrin Cream in October 2017, which was after the start of the conduct of study 71675502 (last patient, last visit occurred on October 30, 2017). Therefore, this protocol was revised to accommodate recommendations in that Guidance, as appropriate. Key revisions are the following:

1. Revised definition of the per-protocol (PP) population to include those patients that are treatment failures on Day 14 as Therapeutic Failures in the final analysis (see section 11.3.1).
2. Revised definition of the Safety population (see section 11.3.2).
3. Removed the secondary efficacy endpoint (see section 11.5).
4. Removed the Yates' continuity correction for calculation of 90% confidence intervals on the absolute difference between the proportion of patients who are considered a Therapeutic Cure in the Test and Reference groups (see section 11.6).
5. Added three supportive analyses to evaluate different evaluation windows for Visit 2 (Day 14) and Visit 3 (Day 28) (see section 11.6).
6. Added descriptive statistics for the number and frequency of re-infestations from Day 14 (Therapeutic Cure) to Day 28 (Therapeutic Failure) in the PP population.

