### 11.2 Determination of Sample Size

For the primary endpoint analysis (proportion of patients in the PP population who are considered to be a Therapeutic Cure on Day 28 ± 4), sample size is estimated for therapeutic equivalence of the Test to the Reference product.

Based on data from a previous bioequivalence study conducted to support approval of the first generic product of permethrin cream, 5%, the therapeutic cure rate ( $p_R$ ) of the Reference product (Elimate™ permethrin cream 5%) is expected to be about 88% in the PP population. Assuming that the Therapeutic Cure rate for the Test group ( $p_T$ ) is an absolute difference of 5% lower than the Reference

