## CONFIDENTIAL PROTOCOL

A Randomized, Double-Blind, Parallel-Design, Multiple-Site Study to Evaluate the Therapeutic Equivalence of Permethrin Cream, 5% (Encube Ethicals) Compared to Elimite™ Cream (permethrin) 5% (Prestium Pharma, Inc.) in the Treatment of Scabies

---

group (i.e.,  $p_T - p_R = -5\%$ ), a sample size of 107 patients in each active group in PP population will provide at least 90% power to demonstrate therapeutic equivalence (i.e., the 90% confidence interval [Yates' continuity corrected] on  $p_T - p_R$  is within a defined equivalence range [-20%, +20%]).

To allow for approximately 14% of patients who may drop out from the study or are otherwise non-evaluable, approximately 250 patients (125 in each treatment group) will be randomized, such that there will be an estimated 214 patients (107 per group) in the PP population for statistical evaluation of therapeutic equivalence.

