8.2 Efficacy Analyses

8.2.1 Primary Efficacy Analysis

Bioequivalence with Clinical Endpoints Analysis

The proportion of patients in each treatment group with Therapeutic Cure is the primary efficacy endpoint of the study.

The Per Protocol (PP) Population will be used for the analysis of equivalence.

Based on the usual method used in OGD for binary outcomes, the 90% confidence interval for the difference in success proportions between test and reference treatment should be contained within [-0.20, +0.20] (or [-20%, +20%] in percent) in order to establish equivalence.

The compound hypothesis to be tested is:

$$H_0: P_T - P_R < -20\% \text{ or } P_T - P_R > 20\% \quad \text{versus}$$

$$H_A: -20\% \leq P_T - P_R \leq 20\%$$

**NOVUM PHARMACEUTICAL RESEARCH SERVICES
STATISTICAL ANALYSIS PLAN**

Permethrin Cream, 5%

Protocol / Study No. 71675502

where P_T = percent cure rate of test treatment
 P_R = percent cure rate of reference treatment.

Let

n_T = sample size of test treatment group
 cn_T = number of cured patients in test treatment group
 n_R = sample size of reference treatment group
 cn_R = number of cured patients in reference treatment group

$$\hat{P}_T = cn_T/n_T \quad \hat{P}_R = cn_R/n_R, \quad \text{and}$$

$$se = (\hat{P}_T (1 - \hat{P}_T)/n_T + (\hat{P}_R (1 - \hat{P}_R)/n_R)^{1/2}$$

where \hat{P}_T = estimated cure rate (%) of test treatment
 \hat{P}_R = estimated cure rate (%) of reference treatment.

The 90% confidence interval for the absolute difference between the proportions of patients in test and reference who are considered a therapeutic cure (primary) will be calculated as follows:

$$L = (\hat{P}_T - \hat{P}_R) - 1.645 se$$

$$U = (\hat{P}_T - \hat{P}_R) + 1.645 se$$

If the 90% confidence interval⁰ for the absolute difference between the proportion of patients who are considered a therapeutic cure (primary) in the Test and Reference groups is contained within the range [-20% + 20%] then bioequivalence of the Test product to the Reference product will be considered to have been demonstrated for the primary endpoint.

Sensitivity Analysis for Primary Efficacy Endpoint

As a sensitivity analysis, the primary efficacy analysis will be performed on the safety population using LOCF. This analysis will use LOCF such that subjects with no post-dose data will be considered as non-responders.

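### Does the Yates-corrected interval in the sample-size text spoil the 90% power claim, when the primary analysis uses an uncorrected interval?

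*SAP*

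**What the plan says.** Three places give the sample-size basis with a corrected interval. SAP section 5 states that 107 per arm "will provide at least 90% power to demonstrate therapeutic equivalence (i.e., the 90% confidence interval [Yates' continuity corrected"]. Protocol 11.2 refers to "the 90% confidence interval [Yates' continuity corrected] on" the difference in cure rates, and the synopsis to "the 90% confidence interval [Yates' continuity-corrected] on" the same difference.

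The analysis is defined differently. SAP 8.2.1 says that the interval for the difference in proportions of patients "who are considered a therapeutic cure (primary) will be calculated as follows": the observed difference plus or minus 1.645 times an unpooled standard error, with no continuity term. Protocol 11.6 speaks only of a 90% confidence interval and mentions no correction.

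The protocol explains the change. Among the key revisions in section 8.3 is "Removed the Yates' continuity correction for calculation of 90% confidence intervals on the absolute difference", and Appendix D lists "Removed Yates’ correction in the primary analysis" under Amendment 1.

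On the planning rate, protocol 8.3 describes the earlier bioequivalence study by "the rate of clinical cure for this product and that for the Reference product", at about 88%. Protocol 11.2 gives the Reference therapeutic cure rate, which "is expected to be about 88% in the PP population".

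**The concern.** The sample-size text and the analysis text name different intervals for the same equivalence decision, and the two sit in one SAP. A reader who stops at section 5 could conclude that a corrected interval decides the trial, and would not learn the power of the interval that does. If the stated power had held only for a more lenient interval than the one in use, the trial could have been too small. If the choice of interval were truly open, a result near the limit could pass one way and fail the other. The mixed labelling of the 88% (clinical cure in one section, therapeutic cure in another) adds some doubt about what the planning rate measures.

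**Working it through.** **Inputs** (protocol 11.2, SAP sections 5 and 8.2.1): Reference rate 0.88; Test rate 0.88 − 0.05 = 0.83; limits ±0.20; z = 1.645; n = 107 per arm in the per-protocol population; non-evaluable about 14%.

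**Standard error**, unpooled as in SAP 8.2.1:

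SE = √[(0.88 × 0.12 + 0.83 × 0.17)/107] = √(0.2467/107) = 0.0480

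**Power** that both limits fall inside ±0.20, with continuity term c:

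Power = Φ((0.20 − 0.05 − c)/SE − 1.645) + Φ((0.20 + 0.05 − c)/SE − 1.645) − 1

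**Step 1: reproduce the plan's figure, with the Yates term.** c = (1/107 + 1/107)/2 = 1/107 = 0.0093.

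- Lower side: Φ(1.284) = 0.9005
- Upper side: Φ(3.367) = 0.9996
- Power = 0.9001, or 90.0%

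With 106 per arm the same formula gives 89.7%, so 107 is the smallest size that reaches 90%. That identifies the stated number as a normal-approximation calculation with the Yates-corrected interval. Exact enumeration of both binomials gives 89.8%.

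**Step 2: the interval that will be used.** c = 0.

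- Lower side: Φ(1.479) = 0.9304
- Upper side: Φ(3.561) = 0.9998
- Power = 0.9302, or 93.0%

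Exact enumeration gives 92.9%. About 94 to 96 per arm would have been enough for 90%.

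| Interval | Approximate power | Exact power |
|---|---|---|
| Yates-corrected (sample-size text) | 90.0% | 89.8% |
| Uncorrected (SAP 8.2.1) | 93.0% | 92.9% |

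**Step 3: what the term does to a result.** It widens the interval by 0.93 percentage points on each side. At observed rates equal to the planning rates, the lower limit is −0.05 − 1.645 × 0.0480 = −12.9% without the term and −13.8% with it. Both are well inside −20%.

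**Step 4: enrolment.** 107/(1 − 0.14) = 124.4, rounded up to 125 per arm or 250 in all, as stated.

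**Step 5: which text governs, and when it changed.** SAP 8.2.1 is the only place with a formula for the interval, and it leaves nothing to choose. SAP section 1 says the SAP is based on the amended protocol, which announces the removal. Protocol 8.3 dates the last patient's last visit to October 30, 2017, and Amendment 1 is dated 10/31/2017. The sample size had therefore been set, and enrolment completed, while the corrected interval was still in the plan.

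**The case for a change.** The best argument for a change is that an equivalence criterion should read the same wherever it appears. The protocol's efficacy section does not name an interval type, so the sample-size text is its only description of the criterion that does, and it names the discarded one. The corrected interval always contains the uncorrected one. At the planning rates, about 3 trials in 100 (92.9% less 89.8%) would pass under SAP 8.2.1 and fail under the criterion as worded in SAP section 5. The text could be tidied in two sentences.

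The inconsistency stands as a matter of wording. It does not stand as a live ambiguity: the phrase is a bracket inside a power statement, whereas SAP 8.2.1 gives the operative formula and protocol 8.3 and Appendix D say that the correction was removed. No analyst following the plan would apply the corrected interval. Nor is any stated figure wrong. The 107 reproduces under the interval the text names, and at least 90% is true of the interval that will be used.

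The labelling of the 88% is a real difference. The documents also do not say whether that rate reflects the current rule that counts Day 14 non-responders as failures (protocol 11.5, SAP section 6). Settling either point needs the cited approval package, which is outside the documents, and nothing in them shows that the rate is below 88%. This is separate from the choice of interval and gives no ground for changing the text here.

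**Conclusion.** No change is needed. The Yates wording in the synopsis, protocol 11.2 and SAP section 5 is a leftover from the interval under which the sample size was set, and it is accurate as a record of that. The planned uncorrected interval has about 93% power at 107 per arm against the stated minimum of 90%, so the mismatch of about 3 points is on the safe side. Rewording would leave the sample size, the analysis and the equivalence decision as they are.

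The conclusion rests on the plan's own rates of 88% and 83% and on 107 evaluable patients per arm. The stated power is conservative only as to the choice of interval. It does not protect against a Reference rate below 88%.
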